8.2.3. Non-invasive instrumental evaluations

8.2.3.1. Tissue dielectric constant of superficial and deep skin layers

The MoistureMeterD measures non-invasively the dielectric constant of the skin and subcutaneous fat. The dielectric constant is a dimensionless physical quantity and it is directly proportional to the water content in the measured tissue. The MoistureMeterD generates a high frequency, low power electromagnetic (EM) wave which the tissue is exposed to. The reflected EM wave is registered and the obtained value is a dielectric constant, which is proportional to the water content of the measured tissue; the measured value increases when water content increases.

The dielectric constant of water molecules depends on the used radiofrequency. Free and bound water behave electrically differently with different frequencies. At around 300 MHz, the electrical properties of free and bound water are quite identical, thus the MoistureMeterD measures changes in the total water content of the tissue.

The measurement depth can be determined by using differently sized probes. There are four probes of different sizes. The corresponding effective measurement depths are 0.5 mm, 1.5 mm, 2.5 mm and 5 mm. The probe should be selected after the measurement site has been determined. The deeper the measurement need the larger the probe. For the present study 0.5 mm and 1.5 mm probes will be used.

8.2.3.2. Skin density evaluation (profilometry)

A little skin area of about 7 cm² (2.5x2.8 cm) at level of the dorsum of the hand is pinched.

A picture of the obtained profile is taken thanks to Primos compact portable device (GFMesstechnik); Primos software is able to elaborate 3D representations of skin wrinkles as well as to measure skin profilometric parameters in vivo or on skin replicas, according to the law DIN EN ISO 4228; moreover the software compares directly the different images obtained at the times foresee by the protocol.

As a measuring method Primos compact uses a digital stripe projection based on micro mirrors which allows for fast and highly precise measuring data acquisition (the speed of under 70ms for the measuring data admission provide perfect results of measurement). An assortment of different measuring fields, realized by means of different precise recording optics ensures a wide spectrum of measuring possibilities with ranges up to micrometers.

8.2.3.3. Torsiometry (skin plastoelasticity)

Torsion is demonstrated to be one of the most effective method used for measuring skin elasticity, being very sensible to skin mechanical properties variation. Measurements will be performed thanks to the instrument Dermal Torque Meter (Dia-Stron Ltd., UK).

By a probe made of two circles adhering to the skin through shaped adhesive tapes, skin surface under-go to a torsion. The distance between the 2 circles delimits the skin area submitted to the mechanical torsion. The internal circle rotation, while the external circle is still, exerts a constant twist of the skin (torsion time = 10 second with a torque = 9mMm); the instrument measures the torsion angle (θ) during the mechanical stimulus ("torque on") and after it stops ("torque off").

For each of the considered curve ("torque on" and "torque off", see Appendix) the cutaneous torque ratio relative to the defined measured times could be measured, obtaining the parameters listed below:

U_e: immediate extensibility ("torque on" at 0.2 sec.)

U_f: final extensibility ("torque on" at 9 sec.)

U_v: viscoelasticity

U_r: immediate elastic recovery ("torque off" at 0.2 sec.)

DERMING S.r.l., Clinical Research and Bioengineering Institute [name]

[contact] - www.derming.com

Test code: E0122

8.2.4. Standard conditions for the treatment evaluations

8.2.4.1. Volunteers

During 3 hours before the visit the volunteer must not drink coffee or alcohol. No cosmetic product can be used on the skin test areas in the 2 hours preceding each visit.

8.2.4.2. Conditions for the measurement execution

All measurements are performed under standard environmental conditions (Temperature=22+/-2°C; Relative Humidity<60%).

8.2.4.3. Acclimatization

Before each visit the volunteer will get acclimatized under relax conditions for at least 10-15 min.

8.3. Evaluation of the treatment efficacy and tolerance (volunteers' judgment)

At the end of the study (T2), each volunteer fills a questionnaire (Appendix 5) regarding:

- the efficacy of the study treatment over skin roughness and laxity of the treated areas, skin suppleness, skin smoothness, skin hydration, skin lifting, contour redefinition/remodeling (score: very marked; marked; medium; light; absent);
- the treatment tolerance (score: bad; poor; good; excellent).

9. TOLERANCE

9.1. Tolerance evaluation

Products tolerance will be evaluated considering:

§ local expected events/reactions induced by the injection procedure (tardive swelling, pain, erythema, bruise);

§ any other adverse event/reaction, also of systemic source occurred during the study.

9.2. Adverse event

9.2.1. Definition and classification

Adverse Event (AE): any untoward medical occurrence, unintended disease or injury, or any untoward clinical signs (including an abnormal laboratory finding) in subjects undergoing a clinical investigation, users or other persons which does not necessarily have a causal relationship with the product under investigation. AEs may manifest as new findings (signs, symptoms, diagnoses, laboratory results) or alterations in pre-existing conditions.

NOTE 1: This definition includes events related to the investigational device or the comparator.

NOTE 2: This definition includes events related to the procedures involved.

NOTE 3: For users or other persons, this definition is restricted to events related to investigational medical devices.

Adverse Device Effect (ADE): an Adverse Device Effect (ADE) is defined as adverse event related to the use of the investigational medical device.

Note 1: This definition includes any adverse event resulting from insufficiencies or inadequacies in the instructions for use, the deployment, the implantation, the installation, the operation or any malfunction of the investigational medical device.

Note 2: This definition also includes any event resulting from user error or from intentional abnormal use of the investigational medical device.

Serious Adverse Event (SAE): an Adverse Event that:

- a) Led to death,
- b) Led to a serious deterioration in health of subject, user, or others that:
- 1) Resulted in a life-threatening illness or injury, or

DERMING S.r.l., Clinical Research and Bioengineering Institute [name]

[contact] - www.derming.com

Test code: E0122

- 2) Resulted in persistent or significant disability or incapacity and/or permanent impairment of a body function or permanent damage to a body structure, or
- 3) Required in-patient hospitalization or prolongation of existing hospitalization, or
- 4) Resulted in medical or surgical intervention to prevent life threatening illness or injury or permanent impairment to a body structure or a body function.

Examples include allergic bronchospasm (a serious problem with breathing) requiring treatment in an emergency room, serious blood dyscrasias (blood disorders) or seizures/convulsions that do not result in hospitalization. The development of drug dependence or drug abuse would also be examples of important medical events.

- c) Led to foetal distress, foetal death or a congenital abnormality or birth defect.

NOTE 1: This includes device deficiencies that might have led to a serious adverse event if

- a) suitable action had not been taken, or
- b) intervention had not been made, or
- c) if circumstances had been less fortunate.

NOTE 2: Planned hospitalization for pre-existing condition, or a procedure required by the Clinical Investigation Plan, without a serious deterioration in health, is not considered a SAE.

The term "life-threatening" in the definition refers to an event in which the subject was at risk of death at the time of the event; it does not refer to an event which hypothetically might have caused death if it was more severe.

Serious Adverse Device Effect (SADE): a Serious Adverse Device Effect (SADE) is an ADE that has resulted in any of the consequences characteristic of a serious adverse event.

Incident:

a) any malfunction or deterioration in the characteristics and/or performance of a device, as well as any inadequacy in the labelling or the instructions for use which, directly or indirectly, might lead to or might have led to the death of a patient, or user or of other persons or to a serious deterioration in their state of health.

b) Any technical or medical reason in relation to the characteristics or performance of a device for the reasons referred to in subparagraph (a), leading to systematic recall of devices of the same type by the manufacturer.

Device Deficiencies (DDs): any inadequacy of a medical device related to its identity, quality, durability, reliability, safety or performance, such as malfunction, misuse or use error and inadequate labelling. A malfunction is failure of an investigational medical device to perform in accordance with its intended purpose when used in accordance with the instructions for use or CIP. A use error is an act or omission of an act that results in a different medical device response than intended by the manufacturer or expected by the user (including slips, lapses, and mistakes). An abnormal use is an act or omission of an act by the operator or user of a medical device as a result of conduct which is beyond any means of risk control by the Manufacturer.

Unanticipated Serious Adverse Device Effect (USADE): Serious adverse device effect which by its nature, incidence, severity or outcome has not been identified in the current version of the risk analysis report.

Definition of the severity of an Adverse Event/Reaction:

The severity/intensity of adverse events/reactions can be graded either on a three-point scale:

- Mild or Grade 1: discomfort noted, but no disruption to normal daily activities.
- Moderate or Grade 2: discomfort sufficient to reduce or affect normal daily activities.
- Severe or Grade 3: inability to work or to carry out normal daily activities.

Relationship with the tested product:

The investigator evaluates the cause-effect relation of each adverse event to the experimental

DERMING S.r.l., Clinical Research and Bioengineering Institute [name]

[contact] - www.derming.com

Test code: E0122

product. Each AE will be classified according to 5 different levels of causality":

- not related
- unlikely
- possible
- probable
- certain

If there is insufficient or incomplete evidence to make a clinical judgment of the causal relationship, the causality can be evaluated as "not assessable". All adverse events judged by either the reporting Investigator or the sponsor as having a reasonable causal relationship to a medical device qualify as adverse device effects.

9.2.2 Categories of Adverse Events

Table 1. Categories of Adverse Events

ADVERSE EVENTS Non-device-related Device- or procedure-related

Non-serious Adverse Event (AE) Adverse Device Effect (ADE)

Serious Serious Adverse Event

(SAE)

Serious Adverse Device Effect (SADE)

Anticipated Unanticipated

Anticipated Serious

Adverse Device

Effect (ASADE) ¹

Unanticipated Serious

Adverse Device Effect

(USADE) ²

¹ ASADE: is an effect which by its nature, incidence, severity or outcome has been identified in the IFU / Manual

² USADE: is an effect which by its nature, incidence, severity or outcome has not been identified in the current version of the IFU / Manual

9.2.3. AEs/Incidents reporting procedure

All incidents and adverse events (AEs) or adverse device effect (ADE) regardless the seriousness must be reported in the source file (if applicable) and in the "Adverse event form" (see "CRF" enclosed in Appendices section). Investigators are responsible for documenting adverse events in the eCRF section created for this purpose.

Moreover, the investigator must determine:

- if the event is serious or not
- if the event is related or not related to the study treatment.

Any adverse event, related or not related to the study treatment, must be documented and will be followed until completed resolution (see paragraph 8.2.3.).

Then, the investigator will decide to:

- interrupt definitively the study treatment
- continue the study as protocol directed
- interrupt temporary the study treatment
- end the study

In case a subject's withdraws from the trial, the form "End of Study" should be filled in and the reasons for discontinuation recorded. The withdrawal subject should be encouraged to attend the final visit for the last study assessment.

9.2.3.1 AEs submission

The investigator must immediately notify to Sponsor (IBSA) all Incidents/SAEs/SADEs occurred during the study by fax, or e-mail and within 24 hours of the investigator becoming aware of the

event to the below dedicated contact details:

IBSA Drug Safety Unit (DSU)

Telephone n.: [name]

Fax n.: [contact] / [name]

Email: [contact]

using the Adverse Event MD form (Appendix 1) provided by the Sponsor.

The Sponsor will confirm the receipt of the concerned Incident/SAE to the investigator by e-mail within 48 hours after the first report was received.

Without acknowledgement of receipt of the e-mail, a letter with acknowledgement of receipt is also sent to the Sponsor accompanied by the form.

Day 0 is the day that the Sponsor receives a notification report from an Investigator and will be the reference to calculate the due date for reporting to the concerned Authorities.

The general provisions for reporting to the concerned Authorities by the Sponsor are into the MEDDEV 2.7/3 guideline.

According that the Sponsor has to notified to Independent Ethics Committee, copying also Ministero della Salute:

a) any SAE which indicates an imminent risk of death, serious injury, or serious illness and that requires prompt remedial action for other subjects, subjects, users or other persons or a new finding to it: immediately, without delay after awareness by Sponsor of a new reportable event or of new information in relation with an already reported event.

b) Any other reportable events, or a new finding or update to it: immediately, but not later than 7 calendar days following the date of awareness by the Sponsor of the new reportable event or of new information in relation with an already reported event.

For the purpose of safety reporting within this study, National Laws must be taken into account and will be mandatory.

9.2.2.2. Incidents submission

The Manufacturer is responsible to assess if a SAE meets the criteria for Incident reporting. If the SAE meets the criteria for Incident Reporting, the Manufacturer will observe all reporting requirements to the Competent Authority and the Notified Body in conformance with the applicable law (European directives 93/42/CEE and 90/385/CE reviewed for directive 2007/47/CE) without delay according to MEDDEV 2.12-1 guideline timelines:

- Serious public health threat: immediately (without any delay that could not be justified) but not later than 2 calendar days after awareness by the Manufacturer of this threat.
- Death or unanticipated serious deterioration in state of health: immediately (without any delay that could not be justified) after the Manufacturer established a link between the device and the event but not later than 10 elapsed calendar days following the date of awareness of the event.
- Others: immediately (without any delay that could not be justified) after the Manufacturer established a link between the device and the event but not later than 30 elapsed calendar days following the date of awareness of the event

9.2.3. Adverse event follow up

All SAEs should be followed-up by the Investigator in order to elucidate as completely and practically as possible their nature and/or causality until resolution of all queries, clinical recovery is complete, laboratory results have returned to normal, stable condition is reached or the subject is lost to followup.

If the study product causes an adverse event, the Investigator could withdraw the subject from the study. During the final visit the Investigator will determine whether the adverse event is ongoing or

DERMING S.r.l., Clinical Research and Bioengineering Institute [name]

[contact] - www.derming.com

Test code: E0122

resolved. In any case it must be followed up to complete resolution.

The Investigator could decide to momentarily suspend the treatment and then to reintroduce it, only if the subject agrees and if the adverse event has been classified “mild/moderate” and its relationship to the study product results unlikely/possible.

All further follow up visits necessary to monitor the adverse event, will be recorded in the adverse event form.

9.2.4. Occurrence of Pregnancy

The investigator must immediately, at the latest within 24 hours from the investigator first notice of the event, inform the Sponsor of the pregnancy using specific form.

Women who become pregnant during the study will be withdrawn from the study but followed until the outcome of the pregnancy is known, and reported to the Sponsor (baby health) using a pregnancy outcome form.

10. SCHEDULE OF STUDY PROCEDURE

10.1. Baseline (T0)

The visit includes:

- detailed explanation of the study procedures and informed consent signature
- filling in the CRF (personal data, subject's history, concomitant medications)
- check of inclusion/exclusion criteria, with particular attention to the assessment of a possible subject's sensitivity to the test product or its ingredients
- pregnancy test (only for women not in menopause)
- clinical and instrumental assessments
- photographic documentation
- 1st injection procedure.

10.2. Intermediate visit (T1 1 month after the 1st aesthetic procedure)

The visit includes:

- record of possible adverse events or intervened illness
- pregnancy test (only for women not in menopause)
- clinical and instrumental assessments
- photographic documentation
- 2nd injection procedure.

10.3. Final visit (T2, 4 months after the 1st aesthetic procedure)

The visit includes:

- record of possible adverse events or intervened illness
- clinical and instrumental assessments
- photographic documentation
- self assessment questionnaire at T2

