1. RATIONALE AND AIM OF THE STUDY

People lose collagen all over the body, not just in the face; skin roughness and laxity of the dorsum of the hands can result from chrono and photo-aging.

This skin roughness and laxity can range from very mild to severe; injection procedures can provide new tone and firmness to the skin of the hand dorsum.

Dermal fillers are the most used non-permanent injectable materials available today to correct skin flaccidity and roughness on the dorsum of the hands. They give immediate aesthetic effect due to elastic gel matrix injected and impart longer term effects due to bio stimulation, promoting new collagen formation.

The objective of this study is to investigate the aesthetic performance of the Hyaluronic acid (HA)-based dermal filler Prohilo® Body injected by a blunt tip microcannula (25G or 22G, preferably 22G), with fanning technique through a single entry point performing 5 passages and injecting 0,3 ml per passage, 1,5 ml for each hand. Volunteers of both sexes, aged 18-65 years with mild-moderate skin roughness and laxity at the level of hand dorsum are to be treated.

Primary endpoint of the study is the evaluation of performance and tolerance of Prohilo Body (3ml) treatment in the back of the hands (or dorsum of the hands).

Secondary endpoint is self-assessment questionnaire by both doctors and volunteers.

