3. STUDY DEVICE

Prohilo® Body (IBSA Farmaceutici Italia S.r.l.) is a resorbable medical device 3.25 ml non-pyrogenic pre-filled syringe, containing 3 ml of 3.2% hyaluronic acid for intradermal use (48 mg H-HA + 48 mg L-HA) dissolved in 3 ml of saline buffered sodium chloride. – IBSA Farmaceutici Italia S.r.l. – ITALY. The principle component is cross-linked Hyaluronic Acid of non-animal origin, produced by bacterial fermentation (see Appendix 1).

On the basis of preceding trials with Prohilo® product, no reaction like injection site reaction, allergies and hypersensitivity reactions (see appendices 1) have been observed. This is due to the fact that this hyaluronic acid is not derived from animal tissue. Some side effects, like little bleeding and/or ecchymosis can happen shortly after injection.

DERMING S.r.l., Clinical Research and Bioengineering Institute [name]

[contact] - www.derming.com

Test code: E0122

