4. DESIGN OF THE STUDY

Open, monocentric.

3 visits, 55 subjects.

T0: inclusion/exclusion criteria**, instrumental and clinical evaluation*, 1° treatment

T1 (after 1 month): instrumental and clinical evaluation, 2° treatment

[figure not shown]
T2 (3 months after T1; 4 months after T0): instrumental and clinical evaluation, NO treatment

Visit number	Study Activities	Treatment
1 T0	
Information and consent form provided. If participants agreeable, to sign consent form.
 
Photographic assessment: - Clinical photography
 
Clinical assessment
 
Instrumental assessment
 
First treatment of Profhilo® (refer to study protocol)
	
Prophilo Body 3 ml 1.5 ml per hand injected by a blunt tip microcannula (25G or 22G, preferably 22G), with fanning technique through a single entry point performing 5 passages and injecting 0,3 ml per passage.

2 T1 (1 month after T0)	
Photographic assessment: - Clinical photography
 
Clinical assessment
 
Instrumental assessment
 
Second treatment of Profhilo® (refer to study protocol)
 
Self-evaluation questionnaire
	
Prophilo Body 3 ml 1.5 ml per hand injected by a blunt tip microcannula (25G or 22G, preferably 22G), with fanning technique through a single entry point performing 5 passages and injecting 0,3 ml per passage.

3 T2 (4 months after T0)	
Photographic assessment: - Clinical photography
 
Clinical assessment
 
Instrumental assessment
 
NO treatment
 
Self-evaluation questionnaire
	No

DERMING S.r.l., Clinical Research and Bioengineering Institute [name]

[figure not shown]
[contact] - www.derming.com

Test code: E0122

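### Tolerance is part of the primary endpoint, but the supplied text schedules no inquiry into reactions that start after the subject leaves until 1 month after injection 1 and 3 months after injection 2, and section 12 names no tolerance analysis or population for it.

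*Combined protocol and SAP*

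**What the plan says.** Section 1 states: "Primary endpoint of the study is the evaluation of performance and tolerance of Prohilo Body (3ml) treatment". Section 9.1 says that tolerance will be judged from "local expected events/reactions induced by the injection procedure (tardive swelling, pain, erythema, bruise"), together with any other adverse event during the study.

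Section 3 reports that in preceding trials "no reaction like injection site reaction, allergies and hypersensitivity reactions" had been observed, but adds: "Some side effects, like little bleeding and/or ecchymosis can happen shortly after injection".

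There are three visits. In section 10.1 the T0 list has no adverse-event item and ends with the "1st injection procedure". In section 10.2 the T1 list opens with the adverse-event record and ends with the "2nd injection procedure". In section 10.3 the final visit again includes the "record of possible adverse events or intervened illness". Section 4 fixes its timing: "T2 (3 months after T1; 4 months after T0): instrumental and clinical evaluation, NO treatment".

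Section 12 covers clinical and instrumental data. Its one population statement (12.2) describes subjects who completed the study as the protocol requires. It contains no sentence on how tolerance will be summarised, or in whom.

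**The concern.** The reactions named in section 9.1 include some that may be short-lived, and section 3 itself places bleeding and ecchymosis soon after the injection. In the schedule, the planned questions come much later. A bruise or swelling that appears at home and has gone by the next visit enters the data only if the subject reports it unprompted or remembers it. After injection 2 the recall period is three times as long as after injection 1.

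What is at stake is the tolerance half of the primary endpoint: incidence, severity and duration of local reactions. The study is open with a single treatment, so no comparator is recorded in the same way. A low reported rate could not be told apart from incomplete capture. The silence of section 12 adds a second weakness: the set of subjects in whom tolerance is reported could be chosen after the data are known.

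**Working it through.** The plan gives no reaction rate and no capture rate, so this is a check of the schedule and of the sample definition, not a power calculation.

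**Step 1: intervals (section 4).**
- Injection 1 at T0, next scheduled adverse-event record at T1: 1 month.
- Injection 2 at T1 (month 1), next scheduled record at T2 (month 4): 4 − 1 = 3 months, which agrees with the interval that section 4 states.
- A subject who completes is asked twice, once after each injection. The record at T1 is listed before injection 2, so it can cover injection 1 only.

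**Step 2: does another provision set an earlier time for asking?**

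| Provision | What it secures | Earlier inquiry? |
|---|---|---|
| 9.2.1, definition of an adverse event | Procedure-related events count | No |
| 9.2.3, reporting procedure | Every event is recorded whatever its seriousness, so a reaction that staff see on site must be recorded | No time for asking is set |
| 9.2.3, follow up | Further visits for an event already identified | No; the event must first be known |
| 9.2.3 (reporting procedure) and 10.4, early withdrawal | A visit with the same content as the final one, which subjects are encouraged to attend | Only for those who withdraw and attend |
| 8.3, volunteer's tolerance rating | One overall four-level score at T2 | No; as described, it has no reaction type, onset or duration |

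The section 4 table also lists a self-evaluation questionnaire at T1. If it is given then, it falls at the same 1-month point and shortens neither interval.

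**Step 3: what remains uncovered.** Taking out reactions seen on site, events reported spontaneously and reactions still present at the next visit leaves one class: non-serious reactions that start after departure and resolve before the next visit. For these, the record rests on recall at 1 month or 3 months.

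**Step 4: population.** Section 5.2 plans 55 enrolled to obtain at least 50 evaluable. If all 55 are treated and 50 complete, 55 − 50 = 5 treated subjects lie outside the sample of 12.2. The number receiving injection 1 would be 55 and the number receiving injection 2 between 50 and 55, so the two injections need separate denominators. The follow-up section lets the investigator withdraw a subject for an event that the product caused. Leaving the completer sample because of a reaction is therefore a route that the plan itself foresees.

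**The case against.** Three objections have force.

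**Completers.** A reader might infer that tolerance will be reported in completers only, and that this could hide up to 5/55 = 9.1% of subjects with a reaction (0/50 reported against 5/55 treated). The documents do not support this. Section 12.2 mentions neither tolerance nor adverse events and sits among provisions for clinical and instrumental data. Section 9.1 takes in any event during the study, with no completer restriction. The figure also needs exactly 5 losses, all with a reaction, and no completer with one. The opposite extreme gives an equal gap the other way: 50/50 = 100% in completers against 50/55 = 90.9% in all treated. Section 5.2 sets a target of at least 50, which is neither a forecast of losses nor a cap on them. What stands is narrower: no tolerance population is named, and if the 12.2 sample were used, subjects who left because of a reaction would be omitted.

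**Unseen appendices.** The adverse-event form, the consent form and the questionnaire (Appendices 2, 3 and 5) may tell subjects to report reactions or may ask for onset and duration. This cannot be excluded, so the point is limited to the supplied text.

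**Existing capture.** The lists in section 10 give visit content and do not say that observation ends with the injection. The general duty to record events is clear, and follow-up of known events is foreseen. It would therefore be wrong to say that the plan has no capture of local reactions. But a duty to record does not reach a reaction that nobody reports or remembers, and none of these provisions sets an earlier time for asking.

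**Conclusion.** The point holds in a limited form. In the supplied text, a non-serious local reaction that begins after the subject leaves and resolves before the next visit has no scheduled inquiry until 1 month after injection 1 or 3 months after injection 2. Followed as written, the plan is likely to under-record or misdate such reactions, more so after the second injection, and this affects a component of the primary endpoint. Section 12 leaves both the tolerance analysis and its population unstated.

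The size of the under-capture cannot be computed, and no percentage should be attached to it. The conclusion rests on two assumptions: that some reactions start and resolve between visits, which fits section 3 but is not quantified there, and that the appendices not supplied do not already ask for this information. It should be fixed, because the remedy is cheap and the missing data cannot be recovered afterwards.

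**What to change.** 1. In 10.1 and 10.2, after the injection item, add a structured eCRF record of the section 9.1 local reactions, completed before the subject leaves.
2. Give each subject a short diary after each injection, its length set by the sponsor, for the same reactions, with the severity grades of section 9.2.1, date of onset and date of resolution. Collect the first at T1. Have the second returned when completed, with T2 as back-up. A scheduled telephone contact is an alternative, but a diary dates onset and resolution directly.
3. In section 12 add: 'Tolerance will be reported in all subjects who received at least one injection, whether or not they completed the study: number and percentage with each local reaction, with 95% CI, and duration, overall and separately after injection 1 (denominator: all who received it) and injection 2 (denominator: all who received it).'

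If Appendix 2, 3 or 5 already asks for any of this, a cross-reference in section 10 is enough for that part.

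Cost: a small amendment, some burden on subjects, diary data entry and staff time to chase the second diary. No extra visit is needed. Reported reaction rates will probably be higher, which the sponsor should expect and explain.
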